### 3.3 Exploratory endpoints

- The quantity of CD3+ T-cells in peripheral blood and in tumor biopsies at each timepoint (baseline, cycle 3, and off-study).
- The expression category in tumor tissue (none (0%), low (<5%), intermediate (5-50%), or high (>50%) of PD-1, PD-L1, PD-L2, CTLA-4, TIM-3, LAG-3 at each timepoint (baseline, cycle 3, and off-study).
- The following T cell subsets will be studied in peripheral blood and tumor tissue: (CD4, CD8, T-reg, CTLA4, TIM3, LAG3, memory, naïve, PD-1, Ki67). For each subset, the absolute change in the relevant marker(s) value will be calculated:
  - Cycle 3 marker value minus Baseline marker value
  - Off-study marker value minus Cycle 3 marker value
  - Off-study marker value minus Baseline marker value

Evaluable criteria:

Eligible subjects who receive at least one cycle of each study drug, and successfully undergo at least one post-treatment core biopsy and blood draw.

- Utilizing each of the alternative (non-RECIST) radiological criteria we will categorize clinical benefit status (CR/PR/SD vs PD). CT and/or MRI with dynamic contrast enhanced sequences will be collected throughout the study at every disease evaluation and analyzed using Choi criteria, MRI volumetrics, and immune-related response criteria. PET/CT will be obtained at baseline, Cycle 3, and off-study and tumor response determined by PERCIST 1.0.

Evaluable criteria:

Eligible patients who receive at least one cycle of each study drug and undergo at least one post-treatment radiographic imaging study.

- The quantity of circulating tumor cells (CTCs) in peripheral blood will be measured at three timepoints: 1. Baseline, 2. Cycle 3, and 3. Off-study.

Evaluable criteria:

Eligible patients who receive at least one cycle of each study drug and undergo at least one post-treatment blood sampling.

- RNA expression of a panel of angiogenesis and immune related genes in tumor biopsies and peripheral blood samples. Expression profiles will be obtained at baseline and at Cycle 3 Day 1 on treatment.

Evaluable criteria: Eligible patients who receive at least one cycle of study drug and undergo at least one post-treated radiographic imaging study.

- T cell clonality indices in tumor and peripheral blood obtained at baseline and at Cycle 3 Day 1.

Evaluable criteria: Eligible patients who receive at least one cycle of study drug and undergo at least one post-treated radiographic imaging study.

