### Analysis for Exploratory Endpoints

Although a large number of factors are being tested, we will not be making adjustments for multiple testing because these analyses are exploratory and hypothesis-generating. Findings will be validated in future larger studies.

Tumor infiltrating T-cells will be quantified by immunohistochemistry using a semiquantitative scoring system as detailed in Appendix F, Section C. We will test for association of clinical benefit status (CR/PR/SD vs PD) vs. T-cell quantity using a Wilcoxon rank sum test. We will test for association with progression-free status at 3 months (progression vs. no progression) vs. T-cell quantity using Wilcoxon rank sum test.

The expression of immune markers such as PD-1, PD-L1, PD-L2, CTLA4, TIM3, and LAG3 by immunohistochemistry will be categorized as negative (0%), low (<5%), intermediate (5-50%), or high (>50%) as detailed in Appendix F, Section C. We will test for association of clinical benefit status (CR/PR/SD vs PD) and expression category using a Chi-square test. We will test for association of expression category vs. PFS using a log-rank test.

To test for the association of the absolute change of each subset (CD4+, CD8+, T-reg, CTLA4+, TIM3+, LAG3+, memory, naïve, PD-1, Ki67) by flow cytometry in blood and tumor tissue between three timepoints (Cycle 3 marker value minus Baseline marker value, Progression marker value minus Cycle 3 marker value, Progression marker value minus Baseline marker value) with clinical benefit status (CR/PR/SD vs. PD), we will use a Wilcoxon rank sum test. Absolute changes across timepoints will be graphically presented for each marker using boxplots.

To test for the association of the absolute change between three timepoints (Cycle 3 marker value minus Baseline marker value, Progression marker value minus Cycle 3 marker value, Progression marker value minus Baseline marker value) of each subset (CD4+, CD8+, T-reg, CTLA4+, TIM3+, LAG3+, memory, naïve, PD-1, Ki67) with progression-free status at 3 months (progression vs. no progression), we will use a Wilcoxon rank sum test.

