
 
Percentage of Malignant cells PD-L1+ (AE1/AE3+PD-L1+)
 
Total T-cell lymphocytes (CD3+)
 
T-cells antigen-experienced (CD3+PD-1+)
 
Cytotoxic T-cells (CD3+CD8+)
 
Cytotoxic T-cells antigen-experienced (CD3+CD8+PD-1+)
 
Total macrophages (CD68+)
 
Macrophages PD-L1+ (CD68+PD-L1+)
 
	
 
Total T-cell lymphocytes (CD3+)
 
Cytotoxic T cells activated (CD3+CD8+Granzyme B+)
 
Effector/memory cytotoxic T cells (CD3+CD8+CD45RO+)
 
Regulatory T cells [(CD3+FOXP3+)-(CD3+CD8+FOXP3+)]
 
	

Figure F2 –

Multiplex immunohistochemistry panels to be performed on tumor biopsies in collaboration with [name] at MD Anderson.

- b. The immune cell infiltrate in the tumor will be assessed according to the intensity and geographic distribution within the tumor. The percentage of the immune infiltrate subset (leukocytes - CD45+, T-lymphocytes - CD3+, macrophages - CD68+) is calculated by dividing the total number of each cell type by the total number of cells present in each 20X microscopic power field. A semiquantitative scoring system for the distribution of the cells is 0-3; 0 = no infiltrate; 1 = focal infiltrate, <5%, mostly perivascular in the tumor with some intratumoral extension; 2 = moderate infiltrate, 5-50%, prominent intratumoral and intermingling with neoplastic cells; 3 = extensive infiltrate, >50%, obscuring tumor cells.
- c. PD-L1 expression (cytoplasmic and cell membrane) by tumor cells and tumor infiltrating immune cells are independently scored by devising a percentage which is calculated by dividing the number of PD-L1 positive specific cells by the total number of each respective cell type. The positivity is scored as negative (0%), low (<5%), intermediate (5-50%) and high (>50%).

- d. PD-1 expression (cytoplasmic and cell membrane) is evaluated in CD3+ T cells using percentage calculated by dividing PD1 positive cells by total number of CD3+ T cells. The positivity is scored as negative (0%), low (<5%), intermediate (5-50%) and high (>50%).
  - e. Statistical analysis and outcomes are detailed in section 16.3.
2. Analysis of tumor biopsies for immunomodulatory markers (Flow cytometry)
- a. 2-4 needle core biopsy specimens will be collected in RPMI media and immediately transferred to [name] laboratory.

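### CD3+ infiltrate, PD-L1 and PD-1 are measured as percentages in Appendix F but tested in Section 16.3 only as four coarse levels, which usually costs power

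*Combined protocol and SAP*

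**What the plan says.** Appendix F, Section A (Exploratory Objective 1), Approach 1, describes three calculations from cell counts:

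- **1.b, immune infiltrate including CD3+ cells:** a percentage "calculated by dividing the total number of each cell type by the total number of cells present in each 20X microscopic power field".
- **1.c, PD-L1:** a percentage "calculated by dividing the number of PD-L1 positive specific cells by the total number of each respective cell type", scored separately for tumor cells and infiltrating immune cells.
- **1.d, PD-1:** a "percentage calculated by dividing PD1 positive cells by total number of CD3+ T cells".

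Each is then graded into four levels with boundaries at 0, 5 and 50%. The T-cell levels form a 0-3 score that also describes where the cells lie. The marker levels are negative, low, intermediate and high.

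Section 16.3 (Analysis for Exploratory Endpoints) uses the graded form: "Tumor infiltrating T-cells will be quantified by immunohistochemistry using a semiquantitative scoring system as detailed in Appendix F, Section C". That score is compared by Wilcoxon rank sum test between clinical benefit groups and between 3-month progression groups. Marker categories are compared by chi-square test with clinical benefit and by log-rank test for PFS. No test on the immunohistochemistry percentages is named. Sections 3.3 and 16.2 describe the T-cell endpoint as a quantity and the marker endpoint as a category.

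**The concern.** A rank test draws its information from the ordering of patients, and a four-level score removes most of that ordering. The middle level spans a tenfold range, from 5% to 50%. If most tumors fall there, the score can hardly separate two groups whose percentages differ clearly.

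Section 16.4 expects about 30 usable sample sets, from biopsies that patients must agree to at three timepoints. It calls the exploratory analysis a critical component of the study. A marker signal missed here would not be carried into the larger studies that Section 16.3 foresees. Appendix F gives no reason for the cut points. In the same section of the plan, flow-cytometry changes and circulating tumor cell counts are tested without being categorised.

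**Working it through.** **Inputs from the documents.** Cuts at 0, 5 and 50% (Appendix F, Section A; Section 16.3). Groups of 10 and 20 (Section 16.4). No multiplicity adjustment for these tests (Section 16.3), so two-sided 5% per test is assumed.

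**The plan's own figure.** Section 16.4 states 89.4% power for a difference in mean change of 2.5, with SD 1 at each time point, correlation 0.2 and alpha 0.05/60.

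- SD of change = sqrt(1 + 1 - 2 × 0.2) = 1.265
- Noncentrality = 2.5 / (1.265 × sqrt(1/10 + 1/20)) = 5.10, with 28 df
- Two-sided noncentral t: 89.4%, reproduced

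That figure concerns a mean change. It does not cover tests on a four-level score, so a separate check is needed.

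**Assumed model.** The percentage is logit-normal, with the higher group shifted by d logit SDs. The values were cut at the plan's boundaries and power was found by simulation.

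**T-cell score, 10 vs 20, no group of exact zeros, d = 1.2.** Twelve settings: lower-group median 2, 5, 10 or 20%, logit SD 0.7 to 1.5, percentages rounded to 1%, 1,000 trials each. Wilcoxon on the percentages had about 80-85% power. Wilcoxon on the 0-3 score had 47-73% in 11 settings and 6% in the twelfth. Repeats with fresh draws gave 44-74% and 5-7%.

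**Why one setting collapses.** Take median 10% and logit SD 0.7. On the logit scale 5% is -2.944, 10% is -2.197 and 50% is 0.

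- Lower group in the 5-50% level: Φ(2.197/0.7) - Φ(-0.747/0.7) = 0.999 - 0.143 = 86%
- Higher group, mean -2.197 + 1.2 × 0.7 = -1.357: Φ(1.357/0.7) - Φ(-1.587/0.7) = 0.974 - 0.012 = 96%

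Nearly everyone is tied.

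**Score and marker chi-square together, 10 vs 20, no exact zeros except in the last row:**

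| Median, logit SD, d | Wilcoxon on % | Wilcoxon on score | Chi-square on 4 levels |
|---|---|---|---|
| 2%, 1.0, 1.25 | 84.4% | 73.5% | 72.9% |
| 10%, 1.5, 1.0 | 65.4% | 56.8% | 45.2% |
| 10%, 1.0, 1.25 | 83.3% | 52.0% | 35.8% |
| 20%, 1.0, 1.0 | 65.2% | 47.3% | 39.5% |
| 2%, 1.0, 1.25, 15% zeros in both groups | 53.8% | 39.6% | 57.3% |

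**Wider grid.** 160 settings: groups 10/20, 20/10, 15/15 and 16/24; medians 2-40%; logit SD 1 or 1.5; d = 1 or 1.25; zeros 0 or 15%.

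- 0-3 score: loss of 6 to 33 points, median 15.
- Chi-square: from a gain of 4 to a loss of 48 points, median loss 15. The loss was 7-35 points in 71% of settings and below 7 in 23%.
- Type I error in a null run was 3.7-3.9% for all three tests, so the gap is not an artefact of test size.

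**Groups that differ mainly in exact zeros.**

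- 5% vs 50% zeros with no shift: 54% on percentages, 58% on the score.
- 10% vs 50% zeros with a 0.5 SD shift: the score loses only 1-4 points.
- 30% zeros in both groups, d = 1.2, median 2%, SD 1: chi-square 42%, Wilcoxon on percentages 32%.

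The log-rank test and a continuous PFS covariate were not simulated.

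**The case against.** The strongest reply has four parts.

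**The 0-3 score is more than a cut percentage.** Its levels also record whether cells are perivascular, intermingled with tumor or obscuring it. That stands: the simulation treats the score as a pure cut, and the spatial reading should be kept. It is no reason to leave the percentage untested.

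**The size is assumption-driven.** This also stands. Absence of infiltrate and 0% positivity are explicit levels in the plan. If presence versus absence carries the signal, the coarse form loses little or does slightly better. The 10/20 split is stated for responders and non-responders, whereas Section 16.3 compares CR/PR/SD with PD and also progression status. The wider grid covers other splits and still shows a loss for the score in every setting.

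**Other analyses may recover the information.** Flow-cytometry changes are tested uncategorised, but that is a different assay and covers change only. The inputs to the penalized logistic regression are not specified, so it cannot be counted on.

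**The analyses are exploratory.** True, and this limits the consequence to lost sensitivity. Section 16.3 itself calls them hypothesis-generating.

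**Conclusion.** The point holds for the CD3+ infiltrate, PD-L1 and PD-1: a percentage is calculated and then only its four-level form is tested. For the T-cell Wilcoxon test the typical cost is about 7 to 35 points of power. This rests on logit-normal percentages with few exact zeros, 10 versus 20 patients, a 1.2 SD shift and two-sided 5%. For the marker chi-square the effect is usually a loss, but ranged from a slight gain to nearly 50 points in the wider grid.

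Three stronger readings are tempting and are not supported:

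- **A percentage is already available for every marker.** Appendix F describes none for PD-L2, CTLA-4, TIM-3 or LAG-3, and PD-L2 and CTLA-4 appear in none of the three multiplex panels.
- **The loss is larger still at alpha 0.05/60 with the 1.98 SD effect (2.5/1.265).** That alpha and effect belong to the mean-change calculation in Section 16.4, while Section 16.3 applies no adjustment to these tests.
- **The stated 89.4% is wrong.** It reproduces for the analysis it describes.

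No primary, secondary or safety conclusion is affected.

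**What to change.** In Section 16.3:

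- Apply the Wilcoxon rank sum test to the CD3+, PD-L1 and PD-1 percentages from Appendix F, for clinical benefit status and for 3-month progression status.
- Enter each percentage as a continuous covariate for PFS.
- State one rule for summarising the 20X fields into a single value per patient, since 1.b defines the percentage per field. For PD-L1, name which cell type is tested, or test both.
- Keep the 0-3 score and the expression categories as descriptive or supportive analyses. This retains the spatial pattern.
- Extend the change to TIM-3, LAG-3, PD-L2 and CTLA-4 only where the laboratory records a percentage.
- Correct the pointer from Section C to Section A of Appendix F, and add the percentages to the objective and endpoint wording in Sections 2.3, 3.3 and 16.2.

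The cost is plan wording and recording a value already calculated. For these three measures no extra tissue, assay or reader is needed. The downside is that percentages from small cores are noisy, and power may fall slightly if the signal is mainly presence versus absence. The retained categories give some cover for that case.

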#### **16.4 Patient Enrollment and Sample Size**

The study will be conducted at Sylvester Comprehensive Cancer Center. Our expectation is that proposed treatment will improve PFS at 3 months from 19% to 40%. Assuming 15 months for enrollment and 12 months minimum follow-up, 40 evaluable patients (including expansion) will provide 97.5% power to reject 3 month PFS rate of 19% in favor of 3 month PFS rate of 40% using a one-sample survival test with one-sided 5% significance level using STPLAN (MD Anderson Biostatistics software) [6]. With estimated accrual of 1 patient every 2 months in the expansion cohort, we anticipate 18-24 months for patient enrollment followed by an additional year of follow up time. Expected time to study completion is 3 years from date open to enrollment.

For the secondary objectives utilizing patient samples, we anticipate that we will be able to obtain complete sets or measurements for all patients (pre-treatment, on-treatment, and post-treatment) to permit analysis of inpatient pharmacodynamic effect of therapy. However, a critical component of this study is the analysis for exploratory endpoints, which are hypothesis-generating in regards to potential biomarkers for response in sarcoma patients treated with concurrent axitinib/pembrolizumab. Thus, if our primary endpoint is met by the conclusion of enrollment and the combination appears active with potential benefit to patients, yet collection of tumor biopsies and peripheral blood sample collection was incomplete, we would consider extending enrollment to an additional 10 patients in an effort to obtain complete paired samples at the baseline, cycle 3, and off-study timepoints in responders and non-responders.

Power considerations for correlative studies: If we estimate 75% collection of complete, interpretable biopsies and blood samples from 40 patients, our analysis set of responders vs. non-responders will include approximately 10 responding patients and 20 non-responding patients. A sample size of 10 in the responder group and 20 in the non-responder group will provide 89.4% statistical power to detect a difference in mean change of 2.5 with a standard deviation of 1 at both time points, and a correlation between two measurement pairs of 0.2. The significance level is 0.00083 using Bonferroni adjustment ( $=0.05/60$ ).

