--	--

Expected Number of Patients	45, including screen failures and non-evaluable patients Expansion cohort: up to 10 additional patients with alveolar soft part sarcoma
Expected Number of Centers	Sylvester Comprehensive Cancer Center (SCCC) Note: SCCC is inclusive of the constituent satellite sites.
Expected Duration of the Protocol	The estimated duration of the protocol is 3 years from screening/accrual to end of follow-up.

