**Study treatment must be initiated within seven (7) days of enrollment.**

## 7.0 STUDY DESIGN

The study will be a single-institution, open-label, single-arm phase II study. Since the primary endpoint is survival outcome (PFS) sample size calculation is based on a single-arm survival design. We will employ early stopping rules for lack of efficacy, based on previously reported historical controls (19% PFS at 3 months) and a large database suggesting that a progression-free rate at 3 months of >40% correlates with an active drug in the second-line setting for patients with advanced sarcoma (43). Patients will be treated with twice daily dosing of axitinib alone for the first 7 days, followed by concurrent axitinib administered twice daily at 5 mg PO twice daily, plus intravenous administration of pembrolizumab every 21 days (Figure 3). Patients will be assessed every three weeks for toxicity. After the first five patients are enrolled, we will assess safety of the combination. If 2 or fewer patients exhibit DLT, we will

then proceed with inpatient titration of axitinib dosing at each cycle based on the presence or absence of predefined toxicities (Section 7.1, Table 3). Correlative studies characterizing T-cells in tumor tissue and in peripheral blood will be performed at three timepoints: 1. pre-treatment, 2. on-treatment on cycle 3 day 1, and 3. off-study. Additional exploratory imaging investigations, and assessment of circulating tumor cells are included for all patients (See Appendix F for complete description of correlative studies).

**Figure 3. Schematic diagram of the study.** The first cycle of treatment will be seven weeks, with one week of axitinib alone prior to initiation of pembrolizumab. Subsequently, six-week cycles of treatment consist of twice daily oral doses of axitinib administered continuously with intravenous (I.V.) administration of pembrolizumab on day 1 and 22. The first five evaluable patients will be considered a safety lead-in, and will not have axitinib dose escalation above 5 mg PO bid. If 2 or fewer patients in the safety lead-in develop DLT, axitinib will then be individually titrated based on toxicity beginning on cycle 2 day 1.

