## 12.2 Evaluations on Treatment

***Collection of Concomitant Medications should occur throughout trial treatment until 30-days ( $\pm 5$  days) post-treatment discontinuation.***

***The collection of Adverse Events (AEs) should occur throughout trial treatment and continue during Follow-up.*** Any SAE, or follow up to a SAE, including death due to any cause other than progression of the cancer under study that occurs to any subject from the time the consent is signed through **90 days** following end of treatment, or the initiation of new anti-cancer therapy, whichever is earlier, whether or not related to the Merck product, must be reported within 24 hours to the Sponsor and within 2 working days to Merck Global Safety. All subjects with SAEs must be followed up for outcome. (See Section 15.0 and Appendix A for details).

**Imaging studies should be done at the beginning of every odd cycle or 12 weeks (every 84 days  $\pm 7$  days) from the date of Registration/Enrollment, timed to coincide with the end of the prior treatment cycle; assessing all known sites of disease using the same type(s) of scan(s) that was/were performed at baseline.**

The appropriate axitinib dosing diary, blood pressure (BP) log monitoring forms and directions' sheet should be given to the patient before each treatment cycle (Appendix I). Afterwards, the dosing diary completed for that (previous) treatment cycle should be collected from the patient. This should be repeated for each cycle.

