12.2.14 Cycle 3, day 1 ( $\pm 3$  days)

The following assessments should be performed on Cycle 3, day 1:

- Note: Imaging Studies (PET/CT, CT and/or MRI) should be repeated prior to treatment every 12 weeks ( $\pm 7$  days) (i.e. every 84 days or subsequent odd cycle). If there are treatment delays leading to the patient being off schedule, scans should coincide with Day 1 of the next cycle as long as within 3 weeks. If delays greater than 3 weeks then scans should be continued every 12 weeks as per schedule.
- Collection/review of previous cycle's patient dosing diary
- PE
- ECOG PS
- V/S
- Weight

- CBC with differential
- CMP, Mg, Phosphate, direct bilirubin
- Coagulation factors
- TFTs
- U/A – (if protein 2+ or greater (grade 2) with no evidence of infection or contaminated sample, obtain urine microalbumin and urine creatinine clearance)
- Urine pregnancy test
- Correlative studies: Tumor biopsy – see Section 13.0
- Correlative studies: PET/CT, Peripheral blood collection – see Section 13.0
- Consideration for axitinib dose escalation; see Section 10.2; **for all subsequent cycles, if a patient is dose-escalated on day 1, they should keep BP log for the first three weeks of the cycle.**

12.2.15 Cycle 3, day 22 ( $\pm 3$  days) – CTU visit, pembrolizumab administration

The following assessments should be performed on Cycle 3, day 22:

- Dosing diary review, BP log reviewed if axitinib escalated on day 1
- CBC with differential
- CMP, Mg, Phosphate, direct bilirubin
- Urine pregnancy test
- If Axitinib dose escalated on (day 1) of this cycle:
  - 12 lead EKG (ONLY if axitinib dose escalation performed)

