## 14.0 MEASUREMENT OF EFFECT

### 14.1 Antitumor Effect in Solid Tumors

For the purposes of this study, patients should be re-evaluated for response every 12 weeks (84 days, ±7 days) from date of Enrollment, (while on treatment and until there is documented evidence of disease progression for those patients who come off treatment). Imaging studies should be timed to coincide with the end of the prior treatment cycle, assessing all known sites of disease using the same type(s) of scan(s) that was/were performed at baseline. Response assessments during follow-up after disease progression should follow the same frequency (every 12 weeks, ±7 days).

Response and progression will be evaluated in this study using the international criteria proposed by the revised Response Evaluation Criteria in Solid Tumors (RECIST) version 1.1 guideline(s). Changes in the largest diameter (unidimensional measurement) of the

tumor lesions and the shortest diameter in the case of malignant lymph nodes are used in the RECIST criteria.

The following general principles must be followed:

1. To assess objective response, it is necessary to estimate the overall tumor burden at baseline to which subsequent measurements will be compared. All baseline evaluations should be performed as closely as possible to the beginning of treatment and never more than four weeks before registration.
2. Measurable disease is defined by the presence of at least one measurable lesion.
3. All measurements should be recorded in metric notation by use of a ruler or calipers.
4. The same method of assessment and the same technique must be used to characterize each identified lesion at baseline and during follow-up.

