#### Analysis for Primary Endpoint

The primary endpoint is progression-free survival (PFS) by RECIST 1.1 in evaluable patients treated with combination axitinib/pembrolizumab. PFS will be analyzed by Kaplan-Meier (KM) methods, and point estimates and 2-sided 95% confidence intervals for PFS will be reported for selected times such as 3, 6 and 12 months from treatment start using Greenwood's variance and the log-log transform method. Median PFS time, if attained, will also be reported.

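### The 97.5% power in Section 16.4 belongs to a one-sample survival test that Section 16.3 does not plan; a 3-month comparison with 19% at n=40 has about 87%

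*Combined protocol and SAP*

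**What the plan says.** Section 16.4 sets a 3-month PFS rate of 19% against 40%, with 15 months of enrollment and at least 12 months of follow-up. It states that "40 evaluable patients (including expansion) will provide 97.5% power to reject 3 month PFS rate of 19" percent, using a one-sample survival test at one-sided 5%. Sections 7.0 and 16.1 also describe the sizing as a single-arm survival design. Section 16.1 still says that Section 16.4 justifies 30 patients, whereas Section 16.4 gives only 40.

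The primary objective (Section 2.1) is to estimate the 3-month PFS rate. The primary analysis in Section 16.3 is Kaplan-Meier: "point estimates and 2-sided 95% confidence intervals for PFS will be reported for selected times such as 3, 6 and 12 months", with Greenwood variance and the log-log transform, plus the median. It names no test, no comparison with 19% and no success threshold. Section 16.4 nevertheless makes a possible extension by 10 patients depend partly on a success criterion: "if our primary endpoint is met by the conclusion of enrollment".

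The date of the first on-treatment scan is described in several ways:
- Section 12.2: "Imaging studies should be done at the beginning of every odd cycle or 12 weeks" from enrollment. Cycle 3 starts 7 + 6 = 13 weeks (91 days) after treatment start.
- Section 14.1: "patients should be re-evaluated for response every 12 weeks (84 days, ±7 days) from date of Enrollment".
- Immediately before Section 7.0: "Study treatment must be initiated within seven (7) days of enrollment".
- Section 12.2.14, for delayed treatment: "scans should coincide with Day 1 of the next cycle as long as within 3 weeks".

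**The concern.** A reader will take 97.5% as the chance that the reported primary analysis succeeds if the true 3-month rate is 40%. The test with that power uses the whole PFS curve, and nearly all 40 patients contribute an event to it. The objective and both hypotheses concern 3 months only, and a 3-month comparison uses less information.

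The undefined criterion matters because two reasonable readings of the plan can disagree on the same data. At 13 of 40 progression-free, 19% is rejected at the one-sided 5% of Section 16.4, but the two-sided 95% interval of Section 16.3 still includes 19%. Progression found by imaging is also dated at 12-weekly scans, so both the survival test and the 3-month status depend on when the first scan falls.

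**Working it through.** **Inputs.** Null 19%, alternative 40%, one-sided 5%, n = 40, accrual 15 months and minimum follow-up 12 months (Section 16.4). Log-log intervals (Section 16.3). Assumptions: exponential PFS, since the documents name no distribution, and uniform accrual.

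**1. The stated 97.5%.** Monthly hazards are −ln(0.19)/3 = 0.5536 and −ln(0.40)/3 = 0.3054, a ratio of 0.552. The event probability under the alternative is 1 − (e^(−12λ) − e^(−27λ))/(15λ) = 0.9945, or 39.8 of 40 patients. The log-hazard test has power Φ(√39.78 × |ln 0.552| − 1.645) = Φ(2.11) = 98.2%. An exact gamma test gives 98.0%, a mean-survival normal test 97.3%, and simulated one-sample log-rank tests about 97.3% to 97.6%. One asymptotic log-rank formula gives 94.7%. The 97.5% is therefore reproduced for exactly dated events.

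**2. A 3-month comparison with 19%, n = 40, all assessable.** Power and size are P(X ≥ r) for X ~ Bin(40, p):

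| Cutoff r | Size (p = 0.19) | Power (p = 0.40) |
|---|---|---|
| 12 | 6.4% | 92.9% |
| 13 | 3.0% | 87.1% |
| 14 | 1.3% | 78.9% |

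The smallest cutoff with size at most 5% is 13. Large-sample approximations give about 88% to 92%.

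**3. The same comparison by log-log limits.** The lower limit is exp(−exp(ln(−ln p̂) + z·se)), with se = √((1 − p̂)/(n p̂))/|ln p̂|. For 13/40, p̂ = 0.325 and se = 0.2027.
- z = 1.645 (two-sided 90%): lower limit 20.8%, above 19%. For 12/40 it is 18.7%. The cutoff is 13, as in the exact test.
- z = 1.96 (two-sided 95%): 13/40 gives 18.8% to 47.0%, which includes 19%. For 14/40 the lower limit is 20.8%. The cutoff is 14, with power 78.9%.

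**4. Effect of the scan date on the 13-of-40 rule.** If status is read at the first scan and scan dates are uniform on days a to b from treatment start, the probability of being progression-free is (e^(−λa) − e^(−λb))/(λ(b − a)), with λ per day.

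| Days from treatment start | How it arises | Probability, null / alternative | Size | Power |
|---|---|---|---|---|
| 88–94 | cycle 3 day 1, ±3 | 0.191 / 0.401 | 3.1% | 87.5% |
| 84–98 | cycle 3 day 1, ±7 | 0.192 / 0.402 | 3.2% | 87.6% |
| 84–91 | 12 weeks to cycle 3 day 1 | 0.204 / 0.416 | 4.9% | 90.9% |
| 77–91 | 84 ± 7, start on enrollment day | 0.218 / 0.431 | 7.7% | 93.6% |
| 70–91 | 84 ± 7, start up to 7 days after enrollment | 0.233 / 0.447 | 11.8% | 95.8% |
| 84–119 | cycle 3 day 1, ±7, delay up to 21 days | 0.161 / 0.363 | 0.8% | 74.4% |

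**5. Reading Kaplan-Meier at exactly 3 months.** Suppose every event is dated at a scan on days 84–98 and the true rate is 19%. By day 91.3, 7.3/14 = 52% of patients have been scanned, and about 80% of those have progressed. The curve then shows 1 − 0.52 × 0.80, or about 58%. This is the extreme case, since deaths are dated exactly.

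**6. Adding the named survival test unchanged.** Scan dating lengthens the recorded times. Against an exactly dated exponential null, simulated type I error across the six windows is about 33% to 47% if a quarter of events are scan-dated and 83% to 96% if half are. The documents do not give that share.

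**The case against.** The strongest reply is that nothing has been miscalculated. Section 16.4 gives a null, an alternative, a side, an alpha and a test; Sections 7.0 and 16.1 repeat the survival design; and the primary endpoint being met can naturally be read as rejection by that test. The stated objective is to estimate, and Section 16.3 delivers an estimate with an interval. It never says that the 95% interval is to be compared with 19%, so the 78.9% belongs to a rule that nobody wrote. Part of the gap to 87% is discreteness: using the full 5% with a randomised boundary gives 87.1% + (0.0203/0.0339) × 5.76% = 90.6%. A binary 3-month test would be a design change, would not say how patients without a 3-month assessment count, and would be chosen after 30 patients were accrued and ASPS outcomes were known (Section 1.5).

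Much of this stands. It is why the proposed rule keeps the Kaplan-Meier estimate and why its timing must be disclosed. It does not remove the mismatch: the analysis section omits the test, and adding the test unchanged raises the scan-dating problem.

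A reader might infer three stronger things that the documents do not support:
- *That 97.5% is an arithmetic error.* It reproduces for the named test.
- *That the trial is too small.* About 87% is adequate, and nothing here calls for more patients.
- *That the trial has a type I error of 11.8%, or of 33% or more.* Those figures depend on a scan window that has not been fixed, on a scan-dated share that is not given, and on how the 19% benchmark was dated, which is also not given.

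**Conclusion.** The concern holds as a mismatch between the power statement and the planned analysis. The 97.5% should not be read as the power of the Section 16.3 analysis. For a 3-month comparison with 19% at n = 40, power is about 87% at one-sided 5% (attained size 3.0%; approximations 88% to 92%), or 78.9% (size 1.3%) if the reported two-sided 95% interval must exclude 19%. These figures assume that all 40 patients are assessable at 3 months and that status is known at that time. Across scan windows that the text allows, the size of the 13-of-40 rule runs from 0.8% to 11.8% and its power from 74.4% to 95.8%, assuming exponential times and uniform scan dates. The 87% is therefore provisional until the window is fixed. Because the primary objective is estimation, this should be fixed but does not undermine the trial.

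**What to change.** 1. **Section 16.3.** Keep the Kaplan-Meier analysis and add one decision rule at the Section 16.4 alpha: the one-sided 95% lower log-log limit of the 3-month Kaplan-Meier estimate (the lower end of the two-sided 90% interval) exceeds 19%. Without early censoring this is the 13-of-40 cutoff. State how patients without a 3-month assessment count, say that meeting the primary endpoint means meeting this rule, and disclose that it was fixed after the first 30 patients were accrued.
2. **Section 16.4.** Replace 97.5% with the power of that rule: about 87% at n = 40 with complete 3-month status, recomputed for the final scan window.
3. **Sections 12.2, 12.2.14 and 14.1.** Reconcile the first-scan timing, allowing for the 7-day start window stated just before Section 7.0. Read 3-month status at the first scheduled scan within a stated window, not at exactly 3 months.
4. **If the sponsor prefers the one-sample survival test,** Section 16.3 must name it and handle scan-dated progression consistently with how the 19% benchmark was dated.
5. **Section 16.1.** Correct 30 patients to the 40 of Section 16.4.

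Cost: no change in sample size. The stated power becomes less favourable, and the rule must be reported as set during the trial. Item 3 must also be aligned with the enrollment-based 12-week timing for response and stable disease in Section 14.1.
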